In Aim 1 of the R21 phase of the project, we will evaluate the acceptability of the study procedures and further refine the CM reinforcement schedule to ensure that a majority of participants will be adherent, find the study procedures acceptable, and substantially reduce their cannabis use. In Aim 2, we will examine the association between frequency of cannabis use and total amount of cannabis consumed per week.

C.2. Overview of the R21 Study Design and Participant Flow

Figure 1 depicts the R21 study design and participant flow. Interested participants that meet initial eligibility criteria during a phone screen will complete an in-person baseline assessment to determine final eligibility. We anticipate that we will need to complete 24 baseline assessments to enroll a final sample of 18 eligible participants. Eligible participants will complete 2 weeks of *ad lib* monitoring during which time they will use cannabis typically to establish baseline patterns of use. Following the 2-week *ad lib* period, participants will complete the 6-week mobile CM for cannabis protocol aimed at

reducing their cannabis use. Afterwards, participants will return to the laboratory to return equipment and to complete an in-person 8-week follow-up.

Figure 1. R21 Study Design & Participant Flow

C.3. R21 Inclusion/Exclusion Criteria

Inclusion criteria include: (a) cannabis use other than ingested cannabis (i.e., edibles) on ≥ 40 of past 90 days; (b) ability to speak and write fluent English; (c) 18-80 years of age; and (d) willingness to attempt to temporarily reduce cannabis use. Participants will be excluded if they: (a) expect to have an unstable medication regimen during the study; (b) are currently receiving non-study CUD treatment; (c) meet criteria for serious mental illness (e.g., bipolar disorder, schizophrenia); (d) become imprisoned; (e) become hospitalized for psychiatric reasons; (f) become pregnant; (g) report imminent risk for suicide or homicide; or (h) meet criteria for a substance use disorder other than CUD or tobacco.

C.4. Recruitment & Enrollment

We estimate that we will need to recruit 24 participants to meet our overall goal of enrolling 18 eligible participants. Participants will be recruited from the community and from outpatient clinics at Duke

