| | | 2 | \$2.50 | No | | | | | |
| 54 | 1 | \$2.50 | Yes | | \$49.00 | | \$54.00 | \$1520.00 | |
| | | 2 | \$2.50 | Yes | | | | | |
| | 55 | 1 | \$2.50 | No | \$50.00 | | \$55.00 | \$1575.00 | |
| | | 2 | \$2.50 | No | | | | | |
| 56 | 1 | \$2.50 | No | | \$51.00 | | \$56.00 | \$1631.00 | |
| | 2 | \$2.50 | No | | | | | | |

only asked to respond to two daily alarms (instead of three). Note, this decreases the potential amount of money earned.

Seventy-two participants will be randomized using a 2:1 allocation ratio to either the Reduced Use

Condition (n = 48) or a Control Condition (n = 24). Inclusion of a control group will allow clear inferences to be drawn regarding the effects of reduced cannabis use on functional outcomes. Study participation will entail completion of the baseline assessment, completion of the 8-week EMA study, and completion of the 8-week follow-up assessment.

D.2. R33 Inclusion/Exclusion Criteria and Recruitment

Timeline

The final inclusion/exclusion criteria for the R33 phase of project will be identical to the R21 inclusion/exclusion criteria with one exception: Participants who are found to meet criteria for bio-verified sustained abstinence (i.e., all of their saliva tests are negative during the 6-week experimental phase of the study) will be excluded from the statistical analyses to ensure that there is an upper limit on reduced use. Thus, we will exclude any participants who achieve sustained abstinence to ensure that any improvements in functioning observed among participants in the experimental condition are not being driven by inclusion of a subset of participants who achieve sustained abstinence. Please also note that we can exclude up to 12 of the 72 enrolled participants from the statistical analyses (remaining N = 60) and still be adequately powered to conduct all of the proposed analyses.

[figure not shown]
D.3. Diagnostic Reliability and Training of Clinical Interviewers

Interviewers will be trained to conduct the interviews using our standardized laboratory procedures, including rating videotaped interviews and participation in ongoing weekly supervision. These procedures have produced consistently high interrater reliability, with Fleiss' kappa values ranging from .92-.94 in previous studies (Kimbrel, Newins et al., 2017; Kimbrel, Calhoun et al., 2014).

D.4. Participant Reimbursement

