Eligible participants will be trained in the EMA procedures following established procedures at the end of the baseline assessment (Beckham, Calhoun 2013). Participants will then practice with the electronic diary at home for 24 hours. Once the training period is complete, participants will complete an 8-week EMA study in which they will carry the diaries with them on a daily basis. The first 2 weeks of the EMA study will involve daily assessments of cannabis use and participants' functional outcomes during the *ad lib* period to establish baseline patterns of use. During the *ad lib* period, participants will also be asked to perform self-initiated diary readings when they begin cannabis use. When participants begin the diary reading, the phone will set an alarm for 60 minutes later. When the alarm sounds, the participant will use a saliva test kit and upload the readings. Participants will be paid \$5 once per day if they begin a self-initiated reading on that day. On day 15, participants in the Reduced Use Condition ($n = 48$) will begin reducing their cannabis use through participation in the mobile CM for cannabis protocol, whereas participants in the Control Condition ($n = 24$) will receive non-contingent payments based on the mean of two yoked participants' earnings. All participants will continue to provide EMA assessments of their functional outcomes during the 6-week experimental period so that we can study the impact of reduced cannabis use on functioning. Electronic diary data stored on the smart phone are encrypted at rest. Data will be downloaded from the smart phones to duhsnas-pri\dusom_psych\private\irb\[name]\Marijuana.

Table 3. Description and Timing of In-Person Assessments

| MEASURE | DESCRIPTION | BL | End of ad lib | 8-wk |
|--|---|----|----------------------|------|
| Demographic Assessment | PhenX (Hamilton et al., 2011) protocols will assess age (#010101), race (#010601), ethnicity (#010501), gender (#010700), and sexual orientation (#101401). | X | | |
| Structured Clinical Interview for DSM-5 (First et al., 2015) | Will be used to diagnose CUD and other psychiatric disorders based on DSM-5 criteria in order to determine study eligibility and characterize sample. | X | | |
| Columbia Suicide Severity Rating Scale (Posner et al., 2011) | State-of-the-art interview that assesses the full continuum of suicidal behavior. Will be used to determine study eligibility and assess suicidal behavior. | X | | X |

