Participants will be asked at each EMA assessment if they have used cannabis, alcohol, or any other illicit drugs, and, if so, how much of each substance they used. Participants will also be prompted each night (~11pm) to estimate the total amount of cannabis, alcohol, and illicit drugs they used in the past 24 hours. Quantity and potency of cannabis consumed during each EMA assessment will be calculated using van der Pol's methods (van der Pol et al., 2014). Participants will also be given a small scale to use to measure their marijuana stash at the end of each day (to assist them in estimating daily use). If participants report use, they will also be asked if they drove a vehicle within two hours of use. We will also ask participants to report the total number of times they engaged in any form of drugged driving during the past 24 hours at the end of each night. EMA-based assessment of cannabis craving will use an 11-point Likert scale that ranges from 0 = "No urge" to 10 = "Extreme urge" (Buckner et al., 2012). EMA of cannabis withdrawal will be completed with the Marijuana Withdrawal Checklist (Budney, Novy & Hughes, 1999; Budney et al., 2003). In our review of data from the first cohorts, we noticed that participants who do not do at least 10 of the 14 nighttime diary readings during the ad lib period are much less likely to participate in the study fully, and are much more likely to be lost to contact during the treatment phase. Therefore, we would like to include in the treatment phase only those participants who complete 10 of the 14 nightly diaries. Any participant who does not meet this criterion will be withdrawn from the study.

EMA of physical activity will be conducted with the Fitbit Charge 2, a light-weight wristband capable of tracking steps, calorie consumption, and sleep. The Vivofit has been validated previously (Simunek et al., in press) and features a 1-year battery life, making it an attractive alternative to more expensive devices. Our programmer, [name], has already written a program that enables us to capture participants' daily step data via Fitbit's Bluetooth syncing technology.

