Power calculations are based on Hypotheses 1a and 1b and were performed with Power Analysis and Sample Size software (PASS, Version 12: NCSS LLC, Kaysville, Utah). We conservatively estimate that as many as 12 participants could potentially need to be excluded due to sustained abstinence, leaving a minimum of 60 participants available for analysis. The corresponding analyses make use of multilevel data with a total sample of up to 3,360 records (60 participants X 56 daily observations). Because there will only be 7 unique estimates per participant of week-to week change in frequency of cannabis use, a conservative minimum estimate of the effective sample size is 420 (60 participants X 7 weekly

observations). Although these observations are non-independent given clustering within participants, hence the use of MLM, accounting for variation between participants will reduce the error variance in the dependent variables. Thus, the effective sample size will very likely exceed 420. An effective sample size of 420 has 90% power to detect small-to-medium treatment effects equivalent to Cohen's $d = 0.30$ or associations equivalent to $r = .16$.

References

Adkisson, K., Cunningham, K.C., Dedert, E.A., Dennis, M.F., Calhoun, P.S., Elbogen, E.B., Beckham, J.C., & Kimbrel, N.A. (manuscript under review). Cannabis use disorder and post-deployment suicide attempts in Iraq/Afghanistan-era veterans.

Babor TF, de la Fuente JR, et al., 1989. AUDIT The Alcohol Use Disorders Identification Test: Guidelines for use in primary health care (WHO/MNH/DAT 89.4). Geneva, Switzerland.

Beckham, J.C., Adkisson, K.A., Hertzberg, J., Kimbrel, N.A., Budney, A.J., Stephens, R.S., Moore, S.D., & Calhoun, P.S. (manuscript under review). Mobile contingency management as an adjunctive treatment for co-morbid cannabis use disorder and cigarette smoking.

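### The floor of 60 participants and 420 weekly records behind the 90% power allows for sustained abstinence only, so neither figure is a minimum under the plan's own withdrawal and loss rules

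*Combined protocol and SAP*

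**What the plan says.** **Allowance.** D.1 sets the trial size: "Seventy-two participants will be randomized using a 2:1 allocation ratio to either the Reduced Use" or control arm, 48 and 24. E.5 then makes one deduction: "We conservatively estimate that as many as 12 participants could potentially need to be excluded due to sustained abstinence". It presents the 60 who remain as the fewest that could be analysed. D.2 treats the same 12 as the whole margin, stating that "we can exclude up to 12 of the 72 enrolled participants from the statistical analyses (remaining N = 60") while power stays adequate for every proposed analysis. E.5 takes 7 weekly values from each of the 60, calls the resulting 420 a conservative minimum effective sample size, and attaches 90% power for d = 0.30 or r = .16.

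**Other losses the plan describes.**
- D.6.1 reports that early participants who completed fewer than 10 of the 14 nightly ad lib diaries were "much more likely to be lost to contact during the treatment phase". It therefore admits to the treatment phase only those who reach 10, and adds: "Any participant who does not meet this criterion will be withdrawn from the study".
- C.3 lists exclusions that can arise after entry: "d) become imprisoned; (e) become hospitalized for psychiatric reasons; (f) become pregnant". D.2 carries the C.3 criteria into the R33 phase and adds only the sustained-abstinence rule.

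**Missing data.** E.1 expects gaps in the EMA data and relies on multilevel models that use all available records. It gives no loss rate and does not adjust the sample size.

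**The concern.** A minimum has to survive every loss that the plan foresees. Here the full difference between 72 and 60 is assigned to one cause. The figure of 420 needs more still: all 7 weekly values from each of the 60. The documents give no expected rate, allowance or replacement rule for loss to contact, the C.3 events or diary withdrawal.

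The power statement rests on these two counts. If they are not floors, the 90% is a best-case figure presented as a conservative one. The sponsor should already hold the data needed to correct this, because D.6.1 refers to a review of the first cohorts.

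A second question follows from the diary rule. If participants are randomised before the check, removing those who fail it would also be a post-randomisation exclusion from the group comparison.

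**Working it through.** **Inputs from the documents.** N = 72 (D.1); 12 removed for sustained abstinence (D.2, E.5); 7 weekly values per person, namely one for the pooled two-week baseline and six for the experimental weeks (E.3, E.5); two-sided alpha .05 (E); r = .16 with 90% power (E.5).

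**Assumptions, because no rates are given.** Treatment-phase loss is 10% or 20% of the 60. Dropouts keep either 4 of 7 weekly values (leaving about halfway) or none.

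**Reproducing the plan.** 72 − 12 = 60, and 60 × 7 = 420. By Fisher's z, power = Φ(atanh(r) × √(n − 3) − 1.96). With atanh(.16) = 0.1614 and n = 420, this is Φ(3.296 − 1.96) = 90.9%. The stated 90% for r = .16 reproduces.

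**Room below 60.** With 58 complete participants, n = 58 × 7 = 406 and power is Φ(3.240 − 1.96) = 90.0% (89.97% before rounding). Two complete losses beyond the 12 use up the margin.

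**Records and power under loss.** The last column is the r detectable with 90% power, tanh((1.960 + 1.282)/√(n − 3)).

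| Case | Records | Power, r = .16 | Detectable r |
|---|---|---|---|
| Plan | 420 | 90.9% | .157 |
| 10% lost, keep 4 of 7 | 54×7 + 6×4 = 402 | 89.7% | .161 |
| 20% lost, keep 4 of 7 | 48×7 + 12×4 = 384 | 88.3% | .165 |
| 10% lost, keep none | 54×7 = 378 | 87.8% | .166 |
| 20% lost, keep none | 48×7 = 336 | 83.8% | .176 |

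**Diary withdrawals.** Someone withdrawn at the end of the ad lib period has at most one weekly value, the baseline. Each such person therefore costs at least 6 of 7 records, close to the keep-none rows. This applies only if the 72 are counted before the check, and it would add to any treatment-phase loss.

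All these figures follow E.5 in treating the weekly values as the effective sample size. Whether that is right for clustered data is a separate question.

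**The case against.** **The diary rule may not touch the 72.** A reader might infer that it necessarily removes randomised participants. The documents do not support that. D.6 says that "On day 15, participants in the Reduced Use Condition ($n = 48$) will begin reducing their cannabis use", which fixes when the intervention starts but not when allocation happens, and the R33 flow figure is not shown. The order in C.2, with enrolment before the ad lib period, describes the non-randomised R21 phase. If allocation follows the check, diary failures take nothing from the 72 and there is no post-randomisation exclusion. This stands. Loss to contact and the C.3 events during the six treatment weeks would still reduce the 60.

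**The models keep partial data.** This also stands, and it is why the keep-4 rows are shown. D.2 removes only sustained abstainers from the statistical analyses, and C.3 does not say that data already collected from other withdrawn participants are discarded. But 420 assumes complete weekly values, which partial records do not supply.

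**Twelve may be generous.** It is a quarter of the 48 if all fall in the Reduced Use arm. The schedule allows a free day each week, and the four pilot participants reduced use by 18–93%, none by 100%. Unused places could absorb other losses. That is plausible, but the plan does not say so, and four people are little evidence.

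**Worst-case stacking.** A reader might combine 20% diary failure with 20% later loss and a fixed 12 abstainers: 72 × 0.8 × 0.8 − 12 ≈ 34 participants. This goes too far. It presumes the unstated randomisation timing, does not scale the abstainers to a smaller sample, and gives later dropouts no records.

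**Conclusion.** The point holds, at modest size. The subtraction and multiplication in E.5 are exact; the fault is an unstated assumption that nobody is lost except through sustained abstinence. The plan's own text contradicts that assumption whichever way the randomisation timing falls, so 60 and 420 should not be called minimums.

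Under an assumed 10–20% treatment-phase loss, power for r = .16 drops from 90.9% by about 1 to 3 points if dropouts keep around half their records, and by about 3 to 7 points if they keep none. At the mild end (89.7%) the figure still rounds to 90%. The actual size depends on rates that the documents do not give.

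A reader might also cite the power for d = 0.30 at 420 independent records as proof that attrition breaks the calculation: 86.6% with a 1:1 split and 82.4% with the trial's 2:1 split. That shortfall exists before anyone is lost. It is a separate defect and says nothing about the loss allowance.

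**What to change.** - In E.5 and D.2, replace the minimum of 60 and the 420 with figures that subtract expected withdrawal and loss as well as sustained abstinence. Use the rates seen in the R21 cohorts, and say how many weekly values a dropout is assumed to contribute.
- Restate power, or the detectable effect, at those figures.
- In D.1, state whether the 72 are counted and randomised before or after the 10-of-14 diary check. If before, state that data collected from diary-withdrawn participants stay in the multilevel models under their assigned group.

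The cost is wording and one recomputed power statement. The drawback is that the stated power will look slightly less favourable.

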Milestone 3: We will calculate the association between frequency of cannabis use (days) and total quantity of cannabis consumed per week based on participants' EMA data concerning quantity of cannabis use.

If the proposed R21 milestones are met, we will complete the following specific aims during the R33 phase:

R33 Aim 1: Assess the impact of reduced frequency and quantity of cannabis use on functioning.

Hypothesis 1a: Decreased cannabis use will be associated with significant improvements in mental health symptoms, self-efficacy, physical activity, and health-related quality of life.

Hypothesis 1b: Decreased cannabis use will be associated with significant improvements in working memory, impulsivity, and drugged driving.

R33 Supplementary Aim: Explore momentary (e.g., craving, sleep) and between-person factors (e.g., sex, baseline use) that might moderate the association between cannabis use and functioning.

Expected Outcomes: The proposed research will be the first study to systematically assess the impact of reduced frequency and quantity of cannabis use on functioning. As such, these findings will directly inform ongoing efforts to include reductions in illicit drug use as a valid, clinically-meaningful outcome measure in clinical trials of pharmacotherapies for the treatment of CUD and other substance use disorders (Tiffany et al., 2011; Donovan et al., 2011).

A. SIGNIFICANCE

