to stress, trauma, and coping strategies. Participants will be informed about these new study procedures verbally, and the study team member who informs them will provide a note-to-fil indicating so. Participants can refuse to complete these measures. We will ask ongoing participants to complete these measures at their next study visit or follow-up session. When study enrollment begins again, participants will complete these measures at the screening session. We are adding the CAIR Pandemic Impact Questionnaire (Lang, 2020; https://www.nlm.nih.gov/dr2/CAIR-PIQ_scoring.pdf), and another measure, COVID Core Questions, with variables of interest. If a participant endorses any item marked with an asterisk on the COVID Core Questions measure, we will ask them to complete a PTSD Checklist 5 related to that specific event. Finally, we have added a measure designed to evaluate participants' satisfaction with remote study procedures.

E. DATA ANALYSIS PLAN

Multilevel modeling (MLM) will be used to analyze the EMA data. MLM is a technique for analyzing repeated observations of data across multiple individuals. Unlike repeated-measures ANOVA, MLM can incorporate time-varying (Level-1) and time-invariant (Level-2) predictors. MLM can also accommodate imbalanced data and unequal variances. The main conclusions drawn from this study will be based on the pre-specified hypotheses, which will be tested with two-sided statistical tests at an alpha of .05. Analyses will be performed with SAS for Windows (Version 9: SAS Institute, Cary, NC).

E.1. Missing Data.

Although we do not anticipate much missing baseline data, we do anticipate missing values in the EMA data. MLM procedures, which will be used to analyze H_{1A}, H_{1B}, and the supplementary aim, are based on maximum likelihood estimation and use all available data. As such, MLM can accommodate data missing at random. Missing data will be examined to determine whether missingness is random or systematically associated with baseline variables. Those baseline parameters associated with missingness will be covaried. If data are suspected to be missing not at random (i.e., only certain values are likely to be missing), multiple imputation will be used to analyze non-random patterns of missing EMA data (Schafer & Graham, 2002).

E.2. Electronic Diary Compliance and EMA Data Reduction.

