During the 8-week EMA data collection, we will calculate the percentage of responses recorded within 5 minutes of the random prompts. We will exclude responses delayed by longer than 5 minutes from the analyses. Data will be aggregated at the day-to-day level to indicate the following: whether cannabis was used; the total number of joints/grams consumed; mean daily potency; mean daily levels of mental health symptoms, self-efficacy, health-related quality of life, working memory, and impulsivity; whether participants drove while intoxicated; and total amount of physical activity. By using multi-daily records to examine day-level phenomena, we will minimize measurement error related to poor recall and random variability. For the 2-week baseline period and each week of the 6-week experimental period, we will calculate frequency of cannabis use as the number of days used per week. To quantify change in frequency of cannabis use from baseline, change scores will be calculated by subtracting number of days per week of cannabis use during the 2-week baseline from those levels

recorded during each week of the mCM treatment period. A dichotomous variable will also be calculated reflecting whether a given participant achieved at least a 50% reduction in cannabis use during a given week. Thus, the data will be structured such that each participant will have up to 56 rows of data corresponding to each day of the 2-week baseline period and 6-week mCM/non-contingent control. Each row will contain a dichotomous indicator of whether or not cannabis was consumed that day, total quantity of cannabis consumed that day, total THC load of the cannabis used that day, daily estimates of functioning, a baseline estimate of cannabis use, and three variables capturing weekly varying frequency, quantity, and total THC load of cannabis use: the aforementioned dichotomous variable measuring whether a 50% reduction from baseline use was achieved and a change score, with a 0 change-score value for days falling during the 2-week baseline.

E.3. Hypotheses 1a and 1b.

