To examine the effect of reduced cannabis use on functioning assessed with EMA, day-by-day outcome variables will be modeled *via* MLM as a function of treatment group (Level 2), week (Level 1; with the two baseline weeks treated as a single week), and treatment-by-week interactions. Daily consumption (total equivalent number of joints/gram consumed and total potency; Level 1) will be examined as potential covariates. Linear and quadratic time effects will be explored. Week-by-week effects of cannabis reduction will be examined in separate models. We will also examine the effects of reduced use by modeling day-by-day and week-by-week outcomes as a function of week-by-week reductions in cannabis, independent of treatment group. Linear MLM will be used to model normally distributed outcome variables *via* PROC MIXED. Generalized linear MLM will be used to model dichotomous and otherwise non-normally distributed outcome variables *via* PROC GLIMMIX.

E.4. Supplementary Aim.

To examine whether reduced cannabis use moderates or is moderated by other factors (e.g., sex differences), the models examined in Hypotheses 1a and 1b will be modified to include potential Level-1 (e.g., day-to-day craving, sleep) and Level-2 (e.g., sex, baseline cannabis use, self-efficacy) predictors as well as their interactions with week-by-week change in cannabis use. For instance, to determine whether a week-by-week reduction in cannabis use moderates the association of day-by-day cannabis use (or abstinence) with daily working memory, whether or not participants used cannabis that day (Level 1) will be added as a predictor of working memory as will its interaction with week-by-week change in frequency or quantity of cannabis use. This particular model could thus determine whether cannabis users demonstrate greater cognitive functioning on abstinent days when they reduce their cannabis use.

E.5. Power Calculations.

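### H1a and H1b span seven outcome domains with no multiplicity control and no rule for how many must be significant, so the error rate behind the main conclusions is undefined and can exceed .05

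*Combined protocol and SAP*

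**What the plan says.** Section E fixes what the study will conclude from: "The main conclusions drawn from this study will be based on the pre-specified hypotheses". It gives one error rate for them, two-sided .05, in the words "pre-specified hypotheses, which will be tested with two-sided statistical tests at an alpha of .05".

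Under R33 Aim 1 in the Specific Aims, neither hypothesis is a single outcome. H1a expects "significant improvements in mental health symptoms, self-efficacy, physical activity, and health-related quality of life", which is four domains. H1b expects "significant improvements in working memory, impulsivity, and drugged driving", which is three.

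E.2 keeps the domains apart in the analysis file. Its daily variables include "mean daily levels of mental health symptoms, self-efficacy, health-related quality of life, working memory, and impulsivity", and the same sentence adds drugged driving and physical activity, making seven.

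E.3 models the outcomes on group, week and group-by-week, and does not rank them. It adds separate week-by-week models and a second route that relates outcomes to reduction in use regardless of group. On time trends it says: "Linear and quadratic time effects will be explored".

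E.5 bases power on H1a and H1b and quotes 90% for one effect at an effective sample size of 420. The document contains no primary outcome, composite, testing order, alpha split or adjustment. It also has no rule for when a hypothesis with several outcomes counts as supported.

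**The concern.** The alpha is stated for hypotheses, but the tests are run on domains, and nothing connects the two. A reader of the results could treat H1a as supported because one of its four domains reached p < .05, and the plan would not contradict that. The error rate for the claim would then be well above the .05 printed in Section E.

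This matters because of the intended use. The Specific Aims say the findings will feed directly into efforts to have reduced use accepted as a trial outcome for pharmacotherapies, and D.1 presents R33 as the adequately powered test of the central hypothesis. Exploration is assigned to the Supplementary Aim. A single chance positive among seven domains could be cited as confirmatory evidence.

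**Working it through.** **Inputs.** Alpha .05, two-sided (Section E). Four domains in H1a and three in H1b (Specific Aims), carried as seven daily variables (E.2). Effective N = 420, with r = .16 or d = 0.30 at 90% power (E.5). Correlations between outcomes are not given, so a range is assumed. The effective N is taken as stated and not endorsed.

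**The plan's own power figure.** For r = .16, power = Φ(atanh(.16) × √(420 − 3) − 1.960) = Φ(0.1614 × 20.42 − 1.960) = Φ(1.336) = 90.9%. This reproduces the stated 90% for one test. The d = 0.30 figure does not reproduce two-sided (86.7% with 210 per arm, 82.6% at 2:1). That is a separate matter, so the r figure is used below.

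**If any one significant domain is enough.** With m independent true null hypotheses, the chance of at least one false positive is 1 − .95^m:

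- H1a: 1 − .95^4 = 18.5%
- H1b: 1 − .95^3 = 14.3%
- all seven: 1 − .95^7 = 30.2%

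Upper bounds under any dependence are m × .05: 20%, 15% and 35%. For positively correlated outcomes, equicorrelated normal test statistics were simulated (1,000,000 draws), counting draws with any |z| above 1.96:

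| Assumed correlation | H1a (4) | H1b (3) | All 7 |
|---|---|---|---|
| 0 (formula) | 18.5% | 14.3% | 30.2% |
| .3 | 17.4% | 13.6% | 27.2% |
| .5 | 15.6% | 12.6% | 23.0% |
| .7 | 13.1% | 11.0% | 17.9% |
| .9 | 9.4% | 8.4% | 11.4% |

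Every entry exceeds 5%. None of them depends on the number of participants.

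**If all domains must be significant.** The error per hypothesis is at most .05 without adjustment, because a false claim requires at least one true null to be rejected along with all the others. Power is what suffers. If every domain had r = .16 and the tests were independent, joint power would be .909^4 = 68% for H1a and .909^3 = 75% for H1b. Positive correlation would raise these, up to 90.9% at most.

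**With Holm within each hypothesis.** The strictest step uses .05/4 = .0125 (H1a) or .05/3 = .0167 (H1b). Power for r = .16 is then:

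- H1a: Φ(3.296 − 2.498) = 78.8%
- H1b: Φ(3.296 − 2.394) = 81.6%

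Later steps are easier: 85.4% at .025 and 90.9% at .05. With all nulls true and tests independent, the chance of any false positive across both families is 1 − (1 − .0125)^4 × (1 − .0167)^3 = 9.6%, and it is at most 10%. Holm over all seven starts at .05/7 = .0071, where power is Φ(3.296 − 2.690) = 72.8%.

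**The case against.** The strongest reply is that Section E describes the level of each test, and each test has it; no familywise rate is promised. That stands. A reader might infer that the plan states an error rate it fails to deliver, but the text does not go that far. What is missing is the step from tests to hypotheses.

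A second reply is that the outcomes in each hypothesis are joined by a conjunction, so that all must improve. This is a possible reading and it would hold the error per hypothesis at or below .05. But no such rule is stated, and it would make the 90% in E.5 inapplicable.

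A reader might also count scales instead of domains. The diary measures in D.6.1 include several for mental health (K-10, PANAS, self-injury) and two for quality of life (WHOQOL-BREF and the Sheehan scale). A count of about 11 would give 1 − .95^11 = 43.1%. The documents do not establish that count: E.2 lists daily variables by domain and does not say how scales are combined. Seven is the defensible figure.

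Nor can every model in E.3 be assumed to be a confirmatory test at .05. The time trends are worded as exploratory, although the other models are not ranked.

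**Conclusion.** The concern holds as a missing decision rule combined with missing multiplicity control. If one significant domain suffices, the false-positive chance is 18.5% for H1a, 14.3% for H1b and 30.2% over all seven with independent tests. At assumed correlations of .3 to .9 it falls to about 17-9%, 14-8% and 27-11%, still above 5% throughout. These figures rest on the any-one rule, on all nulls being true and on one test per domain. If all domains must be significant, the error is controlled per hypothesis but the stated power no longer applies. Either way the plan has to choose.

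A reader might conclude that a spurious finding is likely. The figures do not support that: all are well below one half. They show a substantial chance, not a probable one.

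**What to change.** In E.3:

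- State that H1a and H1b are separate families.
- Designate one measure and one deciding test for each domain.
- Apply Holm within H1a (four tests) and within H1b (three tests), and claim improvement only for the domains that survive.
- Label the other scales, quadratic terms and additional models as supportive.
- Say openly that this leaves up to about 10% across both hypotheses. If study-wide control is wanted, use Holm over all seven.

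Which model is the deciding test is for the sponsor to settle. The randomised comparison is one candidate, but the hypotheses are worded as associations with decreased use and E.5 counts weekly changes in use, so that choice is not dictated by the multiplicity fix.

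The change is to SAP wording and is best made before outcomes are examined by arm. On the plan's own r = .16 and effective N of 420, power at the strictest Holm step falls from about 91% to about 79% (H1a) or 82% (H1b), and is higher at later steps. Holm over all seven starts at about 73%.
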